1. INTRODUCTION

Drug-drug interaction (DDI) occurs when one drug (perpetrator drug) varies the plasma concentration and the biological outcomes of the second drug (victim drug). Pharmacokinetic drug-drug interaction (PK-DDI) may occur at the level of absorption, distribution, metabolism, or excretion when a co-exposed drug may result in alteration of blood-concentration vs. times profile of one or both drugs. Induction of CYP450 enzymes by the co-administered drug results in a decrease in substrate drug concentration leading to in-efficacy or inhibition of CYP450 enzymes by another drug resulting in prolonged half-lives and/or higher substrate drug concentration that may enhance the potential for side effects. Drug transporters also play a vital role in drug disposition when both co-exposed drugs have an affinity for the same binding site of the transporter, while age, gender, nutritional status, various diseases, genetic polymorphisms, and ontogeny of the metabolic enzyme may also affect the drug metabolism (**Müller and Fromm, 2011, Michalets, 1998**).

Voriconazole is synthetically derived from fluconazole antifungal. Voriconazole (**Fig. 1**), chemically is ([2R, 3S]-2- [2, 4-difluorophenyl]-3-[5-fluoro-4pyrimidinyl]-1- [1 H -1, 2, 4-triazole-1-yl]-2-butanol) and has a broad spectrum categorized as second-generation triazole antifungal. Voriconazole is also called a 14-alpha-sterol demethylase inhibitor, broadly used to manage invasive Aspergillosis and other serious fungal infections. Voriconazole binds to the rate-limiting enzyme and inhibits the CYP450 enzyme, leading to inhibition of ergosterol synthesis and deposition of 14-alpha-methyl sterols such as lanosterol, so the structure of fungi cell membrane disrupts. Voriconazole is a strong inhibitor of CYP51 (fungal CYP enzyme) as compared to fluconazole. It has additional activity against *Candida Albicans*, *Candida kurusei* *Scedosporium*, *Fusarium*, and certain other emerging pathogens. Usually, the first oral administered dose of voriconazole is 400mg, followed by a maintenance dose of 200mg at a 12hr dosing interval, and in some conditions, the loading dose is maintained at 9mg/kg, twice a day (BD). Voriconazole is rapidly absorbed and has mostly 96% oral bioavailability. The Peak plasma concentration (C_{max}) of voriconazole is 5.27mg/L at 400mg and the

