target is achieved in 1-2hr after drug administration. Both C_{max} and AUC are dose-proportional over the range of (200mg-400mg). The volume of distribution is 4.6L/Kg and plasma protein binding is 58%. Terminal elimination half-life ($t_{1/2}$) ranged from 8hr to 15hr and there is no effect over the steady- pharmacokinetics of voriconazole by variation in the timings of administration of dose (morning or evening). Voriconazole is highly metabolized by the hepatic enzyme CYP2C19 and forms a voriconazole-N-oxide as a major inactive metabolite, which has only minimal antifungal activity. Other metabolites also formed such as hydroxyl voriconazole and dihydroxy-voriconazole. Voriconazole shows first pass by enzymes present in enterocytes as well as hepatocytes and major systemic metabolisms occur by cytochrome-P450 enzymes such as CYP2C19, CYP2C9, CYP3A4, CYP3A5, and the 25% metabolism occurs by Flavin containing mono-oxygenase FMO-1 and FMO-3. Renal and Biliary excretion of voriconazole (metabolized form) is about 75%-80% and 20%-25% respectively, whereas, the remaining 2% is excreted in urine as unchanged form. Voriconazole is a potent inhibitor of CYP2C19, CYP2C9, CYP2B6, and CYP3A4 enzymes, present in hepatocytes as well as enterocytes. Voriconazole is a p-glycoprotein (ABCB1) substrate at different levels (intestinal, hepatic, and renal levels) and also it is a weak inhibitor of this transporter. Being a lipophilic drug, Voriconazole would be in the un-ionized form as the pH of the formulation shifts towards a neutral value resulting in enhanced permeation (**Mohanty et al., 2013, Vanhove et al., 2017, Mikus et al., 2011, Herbrecht, 2004**).

Clarithromycin (6-O-Methylerythromycin) is a semi-synthetic macrolide antibacterial agent with a 14-membered ring. The oral bioavailability of clarithromycin parent drug is 52-53% and terminal elimination half-life ($t_{1/2}$) is 8hr (**Logan et al., 1994**). The usually recommended dose in adults of Clarithromycin is 250mg-500mg (P/O) twice a day for 7-14 days in various conditions and in some conditions are also given a single dose of 1000mg. About 53% of a single dose of clarithromycin is excreted in the urine and 40% in feces. The volume of distribution of clarithromycin is estimated to be 191 to 309L and plasma protein binding ranges from 42-72%. Clarithromycin is extensively metabolized by hepatic CYP3A4 and

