2. OBJECTIVES

The main objectives of this study will be

1. To develop a sophisticated, robust, and sensitive quantification method using HPLC for the determination of voriconazole in biological fluids.
2. To measure the pharmacokinetic parameters [i.e., C_{max} , T_{max} , $T_{1/2}$, AUC, etc.] of voriconazole in healthy volunteers of Pakistan.
3. To evaluate the PK-DDI of voriconazole with clarithromycin and to study the impact of clarithromycin co-administration on the pharmacokinetic parameters of voriconazole.
4. To interpret the data statistically.

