Male Pakistani volunteers in good health aged 18-35 years will be enrolled as participants in this study. The selection will be based on: a complete detailed medical

history, clinical examination, voriconazole hypersensitivity test, and evaluation of various biochemical tests like Blood Glucose Level, Hemoglobin (Hb) Level, Serum Glutamic-Pyruvic Transaminase (SGPT) Or Alanine Amino Transferase and Aspartate (ALT and AST, respectively) Level, Urine Test, BUN Level, Albumin to Creatinine Ratio (ACR) Test, Glomerular Filtration Rate (GFR) Level, etc.

Exclusion Criteria

Those volunteers who have a history of voriconazole hypersensitivity reaction, deviation from normal values in the biochemical test report, having any pathology like chronic renal disease, hepatic impairment, and having any cardiovascular, gastrointestinal tract, hematopoietic disorders will be excluded from the study. Alcohol addicted, smokers and volunteers who cannot sign the permission consent form will be excluded from the study.

Collection of Blood-Samples

Blood samples (approximately 3cc) will be collected from overnight fasting inducted volunteers in heparinized tubes at specific time intervals of 0.0 (pre-dose), 0.5, 1.0, 1.5, 2.0, 2.5, 3.0, 4.0, 6.0, 8.0, 12 and 24 hours after administration of two tablets of voriconazole (200mg) either alone or co-administration with clarithromycin (500mg). After taking blood samples, immediately these samples will be centrifuged to separate plasma from blood (RBC) and will be stored at -80°C until analysis.

Samples Analysis

We will develop an RP-HPLC/UV-Vis method for the measurement of voriconazole concentration in biological fluid. The stored samples will be brought back to room temperature by thawing technique and the drug will be extracted from plasma samples with already established extraction solvents and subsequently analyzed with the developed method.

Step-3: Data Assessment and Analysis

In this phase, pharmacokinetic parameters used for PK-DDI assessment will be analyzed statistically using compartment and/or non-compartmental approaches. Assorted pharmacokinetic parameters like C_{max} ($\mu\text{g/ml}$), T_{max} (hrs), $T_{1/2}$ (hrs), $[\text{AUC}]_{0-t}$ ($\mu\text{g.h/ml}$), AUMC ($\mu\text{g.h/ml}$), MRT (hrs), and V_d (L) will be determined

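### Sampling stops at 24 h and AUC0-inf is not specified, so the AUC comparison may understate a clearance interaction if inhibition is sustained, and T1/2 is imprecise

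*Combined protocol and SAP*

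**What the plan says.** The study is a single-dose, two-period crossover. Under Collection of Blood-Samples (section 4), draws are at "0.0 (pre-dose), 0.5, 1.0, 1.5, 2.0, 2.5, 3.0, 4.0, 6.0, 8.0, 12 and 24 hours after administration". Six of the twelve fall between 0.5 and 3 h, and only one comes after 12 h.

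The Introduction says voriconazole's terminal half-life "ranged from 8hr to 15hr and there is no effect over the" timing of the dose. For the interacting drug it says: "The oral bioavailability of clarithromycin parent drug is 52-53% and terminal elimination half-life ($t_{1/2}$) is 8hr". Table-1 pairs voriconazole with a 500 mg clarithromycin tablet.

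Step-3 gives an open-ended list of example parameters: Cmax, Tmax, T1/2, AUC0-t, AUMC, MRT and Vd. It allows compartmental or non-compartmental analysis, or both. Section 2 asks only for "AUC, etc.] of voriconazole in healthy volunteers of Pakistan". The documents contain no AUC0-inf, no primary exposure measure, no rule for choosing terminal-phase points and no report of extrapolated area. Step-2 judges the interaction by comparing parameters between treatments.

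**The concern.** The Introduction expects "inhibition of CYP450 enzymes by another drug resulting in prolonged half-lives and/or higher substrate drug concentration". A longer half-life in the combination period pushes more of that period's area past 24 h than in the voriconazole-alone period. The loss then differs between treatments, so the crossover does not cancel it, and the AUC0-24 ratio moves towards 1.

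T1/2 is also listed and could show a clearance effect, but it would rest on about three late points (8, 12 and 24 h), and so would any extrapolated area.

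At stake is objective 3, the effect of clarithromycin on voriconazole pharmacokinetics. The Literature Review says the authors know of no earlier work on this pair, so readers may have only this estimate.

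**Working it through.** The plan defines no AUC ratio and gives no figure to reproduce. A ratio is used here only to size the bias.

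**Coverage.** 24/8 = 3.0 and 24/15 = 1.6 half-lives.

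**Simple check (one compartment, assumed ka = 2/h, clearance divided by 1.5).** Per unit of dose/volume, AUC0-24 = ka/(ka − k) × [(1 − e^(−24k))/k − (1 − e^(−24ka))/ka], and AUC0-inf = 1/k.
- Half-life 8 h, alone: k = 0.0866, AUC0-24 = 1.045 × (10.10 − 0.50) = 10.03 of 11.54. Combination: k = 0.0578, 1.030 × (12.98 − 0.50) = 12.86 of 17.31. True ratio 17.31/11.54 = 1.5; AUC0-24 ratio 12.86/10.03 = 1.28.
- Half-life 15 h: 14.33 of 21.64 alone and 16.72 of 32.46 in combination. AUC0-24 ratio 16.72/14.33 = 1.17.

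**Fuller check (two compartments, linear).**
- From the Introduction: absorbed dose 0.96 × 400 = 384 mg; half-life 8 to 15 h; clarithromycin half-life 8 h; and "The volume of distribution is 4.6L/Kg and plasma protein binding is 58"%, giving a total volume of 4.6 × 70 = 322 L at an assumed 70 kg.
- Assumed: central volume 30, 45 or 60 L; inter-compartmental clearance 20, 35 or 50 L/h; ka 2/h; true AUC0-inf ratio 1.5.
- Clearance is solved for a terminal half-life of 8, 12 or 15 h, which gives 6, 9 and 9 feasible sets, 24 in all.
- Sustained inhibition: clearance/1.5. Fading: CL(t) = CL0/(1 + I0 × 2^(−t/8)), with I0 tuned to a true ratio of 1.5.
- Areas on the protocol's times use the linear-up/log-down trapezoid, with the terminal slope from the last three points.

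| Ratio read for a true 1.5 (no assay error) | Sustained | Fading |
|---|---|---|
| Exact AUC0-24 | 1.25–1.47 | 1.41–1.50 |
| AUC0-24 on the sampling times | 1.25–1.55 | 1.41–1.58, median 1.49 |
| Sets below 1.5 on the sampling times | 22 of 24 | 14 of 24 |
| Mean absolute error, AUC0-24 | 0.121 | 0.038 |
| AUC0-inf, existing schedule | 1.49–1.59 | 1.49–1.58 |
| Mean absolute error, AUC0-inf | 0.026 | 0.037 |

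Under sustained inhibition the sampled ratio is 1.41–1.53 at 8 h, 1.30–1.55 at 12 h and 1.25–1.44 at 15 h. Sampled ratios can exceed exact ones because the coarse early times misstate the area by different amounts in the two periods. At 12 to 15 h, the area beyond 24 h is 4–27% alone, and in combination 6–39% (sustained) or 4–31% (fading).

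**Precision of T1/2.** For a log-linear fit to 8, 12 and 24 h, the mean time is 14.67 h and the sum of squares is 44.4 + 7.1 + 87.1 = 138.7, with root 11.78. With an assumed 15% assay error (0.149 on the log scale), the relative error of k is 0.149/(11.78k): 22% at 12 h (k = 0.0578) and 27% at 15 h (k = 0.0462). Simulated two-compartment profiles at 12 to 15 h give a spread of 22–29% alone and 24–40% in combination. For AUC0-inf the spread is 6–13% and 6–22%.

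**Non-linear sensitivity.** The Literature Review calls the kinetics non-linear, whereas the Introduction says Cmax and "AUC are dose-proportional over the range of (200mg-400mg"). With saturable elimination (assumed Km 0.5 to 3 mg/L, 45 sets) and fading inhibition, AUC0-24 reads 1.25–1.55 (median 1.45). AUC0-inf reads 1.49–1.99 on the existing schedule and 1.50–1.63 with a 48 h sample. With sustained inhibition, AUC0-24 reads 1.14–1.52.

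**The case against.** The strongest objection is that marked understatement in the linear sets needs inhibition that persists. The protocol describes a single-dose study with a clarithromycin tablet and an 8 h clarithromycin half-life, so fading inhibition is the closer match. There the sampled AUC0-24 ratio has a median of 1.49, and 10 of 24 sets do not understate at all. This stands, and it limits the claim. The documents do not settle how long inhibition lasts, so the sustained case cannot be excluded either.

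Second, the parameter list is only illustrative, compartmental fitting is allowed, and AUMC, MRT and Vd normally need extrapolation or a fitted model. AUC0-inf may well be produced. This also stands: a reader might infer that it will not be computed, but the text supports only that it is unspecified. Leaving the choice of measure until the data are in is still a weakness.

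Third, AUC0-inf extrapolated from 24 h is not a cure. Under fading inhibition it barely lowers the error (0.038 to 0.037), reads high in 23 of 24 linear sets, and with saturable elimination can reach 1.99. Any warning must therefore run in both directions.

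Fourth, a purely first-pass effect raises both periods' curves in proportion and is not attenuated. The stated 96% bioavailability leaves little room for one.

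Last, many inputs are assumed, and modelled Cmax (2.5–4.8 mg/L) stays below the protocol's figure, a Cmax that "of voriconazole is 5.27mg/L at 400mg and the" peak at 1 to 2 h. The ranges show direction and rough size only.

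**Conclusion.** The point holds in conditional form. With a last sample at 1.6 to 3 half-lives and AUC0-t the only interval named, the AUC comparison may understate a clearance interaction if inhibition is sustained: 1.25–1.55 for an assumed true 1.5. If inhibition fades with an 8 h half-life the loss is small. A reader might infer that understatement is likely or certain whatever the mechanism. The documents do not support that, because the single-dose design and the stated clarithromycin half-life point towards the milder case.

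T1/2 for an individual volunteer is imprecise at half-lives of 12 to 15 h, and worse in the combination period. Averaging over volunteers reduces random error in the mean. The sizes depend on the assumed interaction, volumes, inter-compartmental clearance, absorption rate, body weight and assay error. The coverage figure and the missing specification come from the documents alone. The specification should be settled before enrolment.

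**What to change.** (a) Main request. Name AUC0-inf (log-linear terminal extrapolation) and CL/F as the exposure measures for the interaction, and report AUC0-24 beside them. Compute AUMC and MRT from extrapolated areas. Report the extrapolated percentage by profile and arm. State that AUC0-24 may understate a sustained clearance interaction, and that AUC0-inf extrapolated from 24 h may overstate it, especially if elimination is non-linear. This costs a few sentences.

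(b) Optional, mainly for precision. In both periods move one early draw (for example 2.5 h) to 36 or 48 h, chosen once Step-1 has set the assay limit.
- Cost: one short return visit per period, inside the two-week washout, and slightly coarser sampling between 2 and 3 h. The number of draws stays at 12.
- Gain at 12 to 15 h (linear, sustained, 15% error): T1/2 spread falls to 10–13% alone and 11–18% in combination with 48 h, or 15–20% and 17–27% with 36 h. For the mean log AUC0-inf ratio over 24 volunteers (one reading of Table-1), the assay-error standard error falls from 1.8–5.2% to 1.4–2.0% with 48 h, a modest gain.
- Limit: no assay limit is stated. At assumed limits of 0.02, 0.05 and 0.1 mg/L, 48 h is measurable in both periods in 13, 6 and 0 of 24 sets; 36 h in 15, 11 and 5.

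(c) If a late draw is used, compare AUC0-t only over a common t within each volunteer, falling back to 24 h for both periods if the late sample is below the limit in either. In sets where 48 h was measurable only in combination, setting AUC0-24 alone against AUC0-48 in combination read 1.60–1.70 for a true 1.5.

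(d) If no draw is moved, treat T1/2 and MRT as descriptive.

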In recent research conducted on voriconazole with flucloxacillin co-administration in patients having chronic granulomatous disease and influenza-associated aspergillosis, a decrease in plasma voriconazole concentration has been reported. Flucloxacillin induced CYP3A4 enzyme resulting in decreased C_{max} . In this study, the researchers have suggested close monitoring of plasma concentration of voriconazole and avoidance of the combination if possible (**Muilwijk et al., 2017**). A case study of pulmonary aspergillosis patients reported a decrease in voriconazole plasma concentration by co-administration with darunavir (non-

peptidic HIV protease inhibitor). This study report suggested that voriconazole, ritonavir, and darunavir should be given cautiously or combination is avoided **(Becker et al., 2015)**.

Many DDIs occur because voriconazole has variable and non-linear pharmacokinetic behavior. Voriconazole is a CYP2C19 and CYP3A4 enzymes inhibitor as well as a substrate of these enzymes. Enzyme CYP2C19 has genetic polymorphism: poor, moderate, and extensive metabolizers **(Bahar et al., 2017)**. Asian peoples are mostly poor CYP2C19 metabolizers so DDI may be possible in this region and voriconazole may show variable C_{max} because of non-linearity **(Mikus et al., 2011)**. Clarithromycin is CYP3A4 and CYP2C19 enzymes inhibitor and voriconazole are also a substrate and inhibitor of these two enzymes **(Furuta et al., 1999)**. Both drugs share the same enzyme pathway so DDI may be possible. To our knowledge, no work has been done for the evaluation of the effect of clarithromycin on pharmacokinetic parameters of voriconazole to date.

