4. METHODOLOGY

This study will be designed in the following three steps.

Step-1: Development of Quantification Method and Its Validation

In the first phase of the current study, we will develop an HPLC method and validation according to standard guidelines for the quantification of voriconazole in a biological matrix. The first phase of the study will comprise of development and validation of the HPLC method for the identification as well as determination of voriconazole in biological fluids.

Step-2: Evaluation of Pharmacokinetic Drug-Drug Interaction

During the second step, sample collection will be carried out and blood samples will be collected in EDTA or heparinized tubes from the enrolled human volunteers, administered with voriconazole alone or co-administered with clarithromycin at specified periods. Further processing of the sample will be done for extractions and subsequent analysis with the developed analytical method. Evaluation of possible pharmacokinetic drug-drug interaction will be carried out through a comparison of pharmacokinetic parameters.

Study Design and Subject

A study designed for drug interaction will be a single oral dose, open-label, randomized, cross-over study of healthy volunteers. The ethical approval of the protocol will be taken from the local ethical committee of the Pharmacy department, Abdul Wali Khan University, Mardan before initiation. This study will follow the “*ethical principles of the Helsinki declaration for medical research involving human subjects*” and “*good clinical practice guidelines*”. Written consent will be obtained from all included volunteers in the DDI study. The study will be comprised of two treatment sequences with a two-week washout period i.e., given in Table-I;

Sequence	Treatment-1 Group-I (n= 12)	Treatment-2 Group- II (n = 12)
Sequence-1	Voriconazole alone (Vfend® Oral Two Tab, strength of 200mg)	Voriconazole + clarithromycin (Vfend® Oral Two Tab, Strength of 200mg with klaricid® Oral Tab, Strength of 500mg)
Two Week Washout Period		
	Treatment-2	Treatment-1
Sequence-2	Voriconazole + clarithromycin (Vfend® Oral sTwo Tab, strength of 200mg with klaricid® Oral Tab, Strength of 500mg)	Voriconazole alone (Vfend® Oral Two Tab, Strength of 200mg)

Table-1: Two Treatment Sequence, Open Labeled, Cross-Over Study Design for the Pharmacokinetic DDI-Study of Voriconazole with Clarithromycin

Inclusion Criteria

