from plasma drug concentration Vs. time profile. All pharmacokinetic parameters will be evaluated using different pharmacokinetic software like PK-Summit® etc., and for graphical data analysis MS-Excel, Minitab, etc. will be used. Appropriate statistical tests like t-test and analysis of variance (ANOVA) will be performed and data will be presented graphically.

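### Step-3 names example tests on seven unranked parameters but commits to no log-scale within-subject ratio with an interval, which is what objective 3 needs

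*Combined protocol and SAP*

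**What the plan says.** Objective 3 (section 2) is "to study the impact of clarithromycin co-administration on the pharmacokinetic parameters of voriconazole". Section 4 describes a "single oral dose, open-label, randomized, cross-over study of healthy volunteers", with two sequences and a two-week washout. Under Step-2 it adds: "Evaluation of possible pharmacokinetic drug-drug interaction will be carried out through a comparison of pharmacokinetic parameters".

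Step-3 states that "pharmacokinetic parameters used for PK-DDI assessment will be analyzed statistically using compartment and/or non-compartmental approaches". It lists seven parameters (Cmax, Tmax, T1/2, AUC0-t, AUMC, MRT and Vd) without ranking them. The only text on the comparison itself is: "Appropriate statistical tests like t-test and analysis of variance (ANOVA) will be performed and data will be presented graphically".

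On variability, section 3 says that "voriconazole has variable and non-linear pharmacokinetic behavior" and that "Enzyme CYP2C19 has genetic polymorphism: poor, moderate, and extensive metabolizers". The documents give no SD or CV, significance level, target effect or power.

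**The concern.** Objective 3 is a question of size: by how much does clarithromycin change voriconazole exposure? Step-3 names a class of tests, as examples, and stops there. Three things follow.

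- **Size and precision.** The same p-value fits quite different effects. Without an estimate and interval as the stated main result, the study could end with a significance statement that does not answer its own objective. A non-significant result could then be misread as no interaction.
- **Scale.** If subjects differ widely in exposure, as section 3 leads one to expect, those with the highest concentrations dominate the raw paired differences. A raw-scale test then loses power against a log-scale one.
- **Choice after the data.** Parameter, derivation (compartmental or not), scale and model are all open. The conclusion could therefore depend on choices made once the results are known.

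**Working it through.** The plan gives no power, alpha, effect size or SD, so there is no stated figure to reproduce. What follows is illustration.

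**Inputs**
- From the documents: a two-sequence, two-period cross-over; Table-1 shows 12 under each of two groups, read here as N = 24 in total. The layout also allows N = 12, so both are shown.
- Assumed: within-subject CV 30% (range 20–40%), between-subject CV 70% (range 40–100%), two-sided 5% test, all subjects complete.

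**(a) What a p-value leaves open**

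On the log scale, s = √ln(1 + CV²), SE of the log ratio = s·√(2/N), df = N − 2. A result exactly at p = 0.05 has ratio exp(t₀.₉₇₅·SE), and its 90% CI is that ratio divided and multiplied by exp(t₀.₉₅·SE).

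For N = 24 and CV 30%: s = √ln(1.09) = 0.294; SE = 0.294 × √(2/24) = 0.0847; ratio = exp(2.074 × 0.0847) = 1.19; CI factor = exp(1.717 × 0.0847) = 1.157; 90% CI 1.03 to 1.38.

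| Within-subject CV | N = 24: ratio (90% CI) | N = 12: ratio (90% CI) |
|---|---|---|
| 20% | 1.13 (1.02–1.24) | 1.20 (1.03–1.39) |
| 30% | 1.19 (1.03–1.38) | 1.31 (1.05–1.62) |
| 40% | 1.26 (1.04–1.52) | 1.42 (1.07–1.89) |

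So the same p = 0.05 can stand for an increase of 13% or of 42%.

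**(b) Cost of the unstated scale**

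Simulated 2×2 cross-overs, 40,000 per setting: log-normal data, a subject effect plus independent within-subject error, no period effect. Both analyses are paired; only the scale differs.

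| N | Between / within CV | True ratio | Power, log scale | Power, raw paired t-test |
|---|---|---|---|---|
| 24 | 70 / 30% | 1.25 | 71% | 56% |
| 24 | 70 / 20% | 1.25 | 96% | 87% |
| 24 | 70 / 40% | 1.25 | 48% | 35% |
| 24 | 40 / 30% | 1.25 | 71% | 64% |
| 24 | 100 / 30% | 1.25 | 71% | 48% |
| 24 | 70 / 30% | 1.5 | 99.5% | 96% |
| 12 | 70 / 30% | 1.25 | 39% | 28% |

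A paired t-test on logs and a log-scale cross-over ANOVA perform the same here (both 71% in the first row). At a true ratio of 1.0 the raw paired test rejects in about 4% of trials, so it is less efficient but not invalid.

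**(c) A limit on what AUC0-t can show**

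The last sample is at 24 h, and the introduction gives a half-life of 8 to 15 h. Assume one compartment, instantaneous absorption and clearance reduced 1.5-fold, so that the total-AUC ratio is 1.5. The AUC0-24 ratio is then 1.5 × (1 − e^(−24k/1.5)) / (1 − e^(−24k)), with k = ln 2 / half-life.
- Half-life 15 h: 1.5 × 0.523 / 0.670 = 1.17.
- Half-life 8 h: 1.5 × 0.75 / 0.875 = 1.29.

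A conclusion drawn from AUC0-t must therefore be worded as exposure over 24 h.

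**The case against.** The strongest reply is that much of this is missing detail, not a wrong method. A randomized cross-over implies a within-subject comparison, the ANOVA may well be a cross-over ANOVA, and a paired t-test on logs would serve. That stands. A reader might infer that an unpaired analysis is planned, but nothing in the documents points to one, and no loss is charged for it here. A reader might also infer that only p-values will be reported. The documents do not support that either: the parameters are to be determined under both treatments, compared and graphed, so the size would be visible. What is missing is a prespecified summary of it with its precision.

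A second reply is that every CV and the ratio of 1.25 are assumed. That is correct. Most interactions quoted in section 3 are described as changes of 100 to 150%, and at a ratio of 1.5 the scale hardly matters. The non-linear kinetics cited there do not by themselves show between-subject spread. The same section says that Asian people are mostly poor CYP2C19 metabolizers, which could mean a less mixed sample, although it still expects variable Cmax.

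A third reply is that asking for a no-effect range would import an equivalence aim. That also stands. Objective 3 asks for the impact and sets no such aim, so the absence of a range is not a defect. A rule declaring no relevant effect from AUC0-t would also carry the truncation risk shown in the check.

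**Conclusion.** The concern holds as a gap in prespecification that is worth closing; it is not an error in the tests named. The absence of a stated scale, within-subject model, estimate with interval and deciding parameter is certain from the text. The size of the consequence is not, because the documents give no variability.

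Under the central assumptions (N = 24, CVs 70% and 30%, ratio 1.25), a raw scale costs about 15 points of power (71% against 56%). Across the other settings tried at that ratio the gap runs from 7 to 23 points at N = 24, and is 11 points at N = 12. It is about 3.5 points at a ratio of 1.5, and zero if a paired log-scale analysis would be used anyway. In that last case the missing estimate, interval and deciding parameter remain.

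The stronger claims, that the tests are invalid or that the plan must contain a no-effect range, are not supported.

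**What to change.** In Step-3:

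- Name non-compartmental ln(AUC0-t) and ln(Cmax) as the parameters that carry the conclusion.
- Analyse them within subject by cross-over ANOVA with sequence, subject within sequence, period and treatment.
- Report the geometric mean ratio (combination over alone) with its 90% CI as the main result.
- Treat the other parameters as descriptive, with a paired non-parametric method for Tmax, and keep compartmental fits supportive.
- State that a non-significant result is not evidence of no interaction.
- State that AUC0-t conclusions apply to exposure over 24 h, and report AUC0-inf and the extrapolated fraction as supportive.
- Optional: if the sponsor wishes to claim no relevant effect, set and justify a no-effect range before the data are seen.

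The cost is wording and slightly more analysis work on the same samples. The downside is that an imprecise result must be reported as imprecise.

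### No method is specified for Tmax, and the only tests named compare means, so a few late peaks could hide a consistent delay; a rank-based crossover comparison is a minor, cheap improvement

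*Combined protocol and SAP*

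**What the plan says.** All references are to section 4 (Methodology) of the combined protocol and SAP, except the last.

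- **Design.** Study Design and Subject describes a "single oral dose, open-label, randomized, cross-over study of healthy volunteers". Table-1 has two sequences and labels its columns in the style "Treatment-1 Group-I (n= 12" (closing bracket omitted here). This can be read as 12 volunteers per sequence or as 12 in all.
- **What is compared.** Step-2 judges the interaction by comparing pharmacokinetic parameters, with no exception for Tmax. Step-3 lists Tmax as one of seven parameters, each derived "from plasma drug concentration Vs. time profile" using "compartment and/or non-compartmental approaches".
- **Sampling.** Collection of Blood-Samples gives "0.0 (pre-dose), 0.5, 1.0, 1.5, 2.0, 2.5, 3.0, 4.0, 6.0, 8.0, 12 and 24 hours".
- **Tests.** Step-3 states "Appropriate statistical tests like t-test and analysis of variance (ANOVA) will be performed". It names no scale (raw or log), model terms, alpha or confidence level for any parameter, and no rank-based test appears anywhere.
- **Expected peak.** Section 1 (Introduction) says the peak "target is achieved in 1-2hr after drug administration".

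**The concern.** With an expected peak at 1-2 h, most observed Tmax values should fall at 1.0, 1.5 or 2.0 h. An occasional late peak would then sit hours away from the rest. A test on raw means gives such a value its full weight twice: it moves the mean difference and it inflates the standard error. One or two late peaks on the voriconazole-alone arm could therefore cancel a delay seen in most volunteers.

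Tmax bears directly on the rate of absorption, and the Introduction discusses intestinal transporters and gut-wall enzymes as possible sites of interaction. A report of no change in Tmax could then rest on one volunteer's profile. Because the study is open-label and the choice of test is left open, the method is better fixed before the data are seen.

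**Working it through.** The documents give no alpha, power, effect size or SD for Tmax, so there is no stated figure to reproduce. Two checks were made, both on within-volunteer period differences (period 2 minus period 1) compared between sequences. The t-test on these is the standard 2x2 crossover test. The rank-sum test on them is its rank-based counterpart. Both allow for a period effect.

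**1. Worked example on the protocol's sampling times (12 per sequence, no period effect)**

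Each volunteer's shift is Tmax on the combination minus Tmax on voriconazole alone. In one sequence the period difference equals this shift; in the other it is the shift with its sign reversed. The treatment effect is half the difference between the sequence means.

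*No late peak.* Each sequence has 8 volunteers at +0.5 h and 4 at 0.
- Mean shift = 16 × 0.5 / 24 = 0.33 h.
- Sum of squares per sequence = 8 × 0.25 − 12 × (1/3)² = 0.667. Pooled variance = 1.333/22 = 0.0606.
- SE = √(0.0606 × 2/12) = 0.1005. t = 0.667/0.1005 = 6.63 on 22 df, p < 0.001.
- Rank-sum: p < 0.001.

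*One late peak.* One unchanged volunteer instead peaks at 6 h alone and 2 h on the combination (−4 h).
- Mean shift = (16 × 0.5 − 4)/24 = 0.17 h.
- That sequence now has mean (8 × 0.5 − 4)/12 = 0 and sum of squares 8 × 0.25 + 16 = 18. Pooled variance = (18 + 0.667)/22 = 0.848.
- SE = √(0.848 × 2/12) = 0.376. t = 0.333/0.376 = 0.89, **p = 0.38**.
- Rank-sum, with midranks 1 (one value), 5.5 (eight), 13 (seven) and 20.5 (eight): W = 1 + 3 × 13 + 8 × 20.5 = 204, against 12 × 25/2 = 150 expected.
- Tie-corrected variance = [144/(24 × 23)] × 1038 = 270.8, SD 16.46. With continuity correction z = 53.5/16.46 = 3.25, **p = 0.001**.

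*Two late peaks, one in each sequence.*
- Mean shift = (16 × 0.5 − 8)/24 = 0.00 h; t-test p = 1.00; rank-sum p = 0.008.

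**2. Simulated power for a true 0.5 h delay**

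From the documents: the sampling times, the crossover design, 12 per sequence (one reading of Table-1), and a peak at 1-2 h, taken as a median of 1.5 h. Assumed, not in the documents: lognormal Tmax, log-SD 0.25 between and 0.25 within subjects, two-sided 5% tests, a 0.5 h delay, and a stated share of profiles peaking at 4, 6 or 8 h. Tmax was rounded to the nearest scheduled time.

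| Late peaks | Raw t-test | Rank-sum |
|---|---|---|
| none | 96% | 96% |
| 5% | 43% | 79% |
| 10% | 24% | 56% |

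- **Log scale.** At 5% late peaks a t-test on log Tmax has about 73% power.
- **Within-subject log-SD, 5% late.** At 0.15: 47% vs 94%. At 0.35: 36% vs 58%.
- **Only 12 volunteers in all (6 per sequence), 5% late.** About 35% vs 40% with a continuity correction in the rank test; 36% vs 46% without it.
- **Is the grid the cause?** At 5% late peaks the raw t-test has 43% power with rounding to the scheduled times and 44% without. It is not.
- **No true shift.** Rejection rates are 2-5% (t-test) and 4-5% (rank-sum).

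**The case against.** The strongest counter-arguments, and what stands of each:

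- **The plan does not assign the t-test to Tmax.** This stands. The Step-3 sentence gives examples and asks for tests that are appropriate. A reader might infer that Tmax must be compared by t-test or ANOVA; the text does not say so. What remains is that both examples compare means and nothing is specified for Tmax.
- **The scheduled times are not the problem.** This stands. A reader might infer that the uneven grid causes the loss, or makes a mean difference meaningless. Rounding costs the raw t-test about one percentage point, a move from 2 to 6 h shifts a mean of 24 by 4/24 = 0.17 h on any grid, and a mean difference in hours remains a mean difference. Nor is Tmax necessarily confined to scheduled times: the plan also allows a compartmental approach, under which a model-derived Tmax is continuous.
- **Late peaks may be rare.** This stands as a limit on size. The documents give no late-peak rate. They state a 1-2 h peak, fasted dosing, healthy men, and exclusion of gastrointestinal disorders. Without late peaks the raw t-test loses nothing. The worked example, however, needs only one late profile among 48.
- **A log-scale t-test would recover much of the power.** This stands: 73% against 79% for rank-sum. But the plan states no scale.
- **Tmax is secondary to the question.** This largely stands. No primary endpoint is named, and the Literature Review rests the rationale mainly on shared enzyme pathways, for which AUC and Cmax carry more weight.

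**Conclusion.** The point holds as a minor one. Tmax is to be compared, only mean-based tests are named, and no method is specified for it. On the raw scale, one late peak among 24 volunteers is enough to take a consistent delay from p < 0.001 to p = 0.38, while the rank-sum test stays at p = 0.001.

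The power loss at 5% late peaks, about 43% against 79%, depends on the assumed late-peak rate, variability and delay. It shrinks to about 35% against 40% if Table-1 means 12 volunteers in all, and vanishes if there are no late peaks. The direction was the same in every setting with late peaks.

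The harm is a missed delay, not a false one. A reader might infer that the overall interaction conclusion is at risk; the documents do not support that, because only the Tmax comparison is affected.

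**What to change.** Add one sentence to Step-3 with this content: observed (non-compartmental) Tmax will be reported as median and range by treatment, and compared by a tie-corrected or exact Wilcoxon rank-sum test of within-volunteer period differences between the two sequences, with a Hodges-Lehmann estimate and 90% CI. The t-test and ANOVA stay for the other parameters.

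The estimate is half the median of all pairwise differences between the sequences' period differences (12 × 12 = 144 pairs with 12 per sequence).

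**Cost.** No new data, visits or samples. The estimate is less direct than a mean difference, and ties make it and its CI limits coarse. In the one-late-peak example, 12 of the 144 pairwise differences are negative, 12 are zero, 56 are 0.5 h and 64 are 1 h. Their median is 0.5 h, so the estimate is 0.25 h although two thirds of volunteers shifted by 0.5 h. It is the same 0.25 h with no late peak (16 at zero, 64 at 0.5 h, 64 at 1 h), whereas the mean shift falls from 0.33 to 0.17 h.
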